1.3.2 Potential Benefits

Participants are not expected to receive any personal benefits from being in this study.

OBJECTIVES

1.4 **Study Objectives**

The purpose of this study is to assess tooth health by using a pulse oximeter which measures the blood flow within the tooth. We hypothesize that if we can measure both sensation and blood flow in a tooth, we will be able to better determine if the tooth is "alive or dead". In the future, this method may help determine which teeth are diseased and require dental treatments.

Our specific aims are:

Aim - 1: To measure pulpal blood flow using pulse oximeter and Laser Doppler Flowmeter

Aim - 2: To measure tooth vitality using Cold, Electrical Pulp tester (EPT) , percussion and palpation testing

Aim - 3: To assess histological presentation of the pulp the extracted teeth

Aim - 4: To evaluate the relationships between the Aims 1-3 to determine if pulpal blood flow is a reliable indicator of tooth vitality.

1.5 **Study Outcome Measures**

Primary Outcomes Measures: Correlation Between Subjective and Objective Measurements of Pulpal Status

- Subjective Measurements Pulpal Status: Conventional pulpal diagnosis using cold test [Endo Ice, Coltene/Whaledent, Cuyahoga Falls, OH, USA] and Electrical Pulp Test -EPT S[Kerr Vitality Scanner, SybronEndo] testing and recorded, along with vertical and lateral percussion and palpation responses. Conventional pulpal diagnosis assessment would be used for teeth that are planned for extraction and additional teeth (10 total) in each participant
- *Objective Measurements Pulpal Status:* Measurements obtained from pulse oximeter gives a series of reading of oxygen saturation level, and pulse. Pulse oximeter measurements would be used for teeth that are planned for extraction and also up to 2-5 additional teeth in each participant

Exploratory Outcomes:

- *Systemic Vital Sign Measurements:* Blood pressure and pulse recording will be obtained from the recorded values from the participant's chart.
- *Histological Assessment of the Extracted Teeth:* Upon completion of extraction, the teeth will be placed in formalin-containing bottle. After formalin fixation, the teeth will be prepared for histological examination using 10% EDTA for demineralization. Following that, the teeth are trimmed, embedded in paraplast and cut longitudinally to obtain 6um thick section. The sections were stained with H&E and examined with a light microscope.

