- 6. Must have at least two teeth with an intact crown, without any full metallic crown coverage, and/or previous root canal treatments
- 7. Must have no history of spontaneous pain, and/or lingering pain to cold/hot in teeth that are not going to be extracted on that day.
- 8. If one of the teeth mentioned in inclusion #6 is being extracted, be willing to give your extracted tooth/teeth for further analysis to determine of the tooth is "alive or dead"

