1.20 Study Hypotheses

The calculations are based on a comparison of the test results and "true" disease status. The sensitivity, specificity, and positive and negative predictive values of heat and cold application and electrical pulp tests will be calculated. Teeth are grouped into two categories, healthy, true disease (irreversible pulpitis and necrosis). A perfect diagnostic test would always be positive in the presence of disease and negative in the absence of disease. Therefore, sensitivity, specificity, and positive and negative predictive value have been developed to characterize test accuracy and to compute the benefits of test usage. In addition to that, clinical measurements of the extracted teeth will be compared with identification of the true disease by histological evaluation for the pulp status.

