1.22 Final Analysis Plan

To compare accuracy of pulp vitality between traditional tooth vitality testing (Cold and EPT) to pulse oximeter reading to determine if the pulse oximeter is a reliable indicator of tooth vitality. We will analyze the relationships between these clinical readings using Pearson correlations and/or Chi Square tests. We will evaluate repeatability of the measurements within a tooth for the pulse oximeter using Bland-Altman plots, intraclass correlation coefficients (ICCs), and the percentage of repeat measurements within +/- 0.5 mm along with a 95% confidence interval for the percentage. Pulse oximeter reading will be compared against the gold standard (Cold and EPT) assessment using paired t-tests, 95% confidence intervals for the difference from the gold standard with a 95% confidence interval. The clinical pulpal status will be compared to the histological status for the difference using ANOVA and compared for the percentage of measurements with +/- gold standard visual assessment of the pulp status using McNemar's tests.

SOURCE DOCUMENTS AND ACCESS TO SOURCE DATA/DOCUMENTS

Study staff will maintain appropriate dental and research records for this study. Study staff will permit authorized representative and regulatory agencies to examine (and when required by applicable law, to copy) research records for the purposes of quality assurance reviews, audits and evaluation of the study safety, progress and data validity.

QUALITY CONTROL AND QUALITY ASSURANCE

Quality control will be continually monitored by periodic (semi-annual) reviews of the protocol and procedures used in the study. All questionnaire data is reviewed on the day of the participant visit for completeness. De-identified data is monitored after collection for various points of quality assurance.

ETHICS/PROTECTION OF HUMAN SUBJECTS:

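### Section 1.20 does not define the source of 'true' pulp status or the teeth it covers; if cold and EPT supply it for non-extracted teeth, their accuracy estimates are circular

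*Combined protocol and SAP*

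**What the plan says.** - Section 1.20 (Study Hypotheses) opens its accuracy calculation with "The calculations are based on a comparison of the test results and" a disease status that the plan itself puts in quotation marks as true. Sensitivity, specificity and "predictive values of heat and cold application and electrical pulp tests will be calculated". Teeth are split into healthy and truly diseased (irreversible pulpitis and necrosis). The section does not say how a tooth is assigned to a group, or whether only extracted teeth are used.
- The histology comparison comes at the end of the same section as an addition: "In addition to that, clinical measurements of the extracted teeth will be compared with identification of the true disease by histological evaluation".
- Section 1.22 (Final Analysis Plan) names a reference for the oximeter: "Pulse oximeter reading will be compared against the gold standard (Cold and EPT) assessment using paired t-tests". It also mentions a gold-standard visual assessment of the pulp, which it does not define.
- Section 1.5 (Study Outcome Measures) builds the conventional pulpal diagnosis from cold and EPT, recorded with percussion and palpation: "Conventional pulpal diagnosis assessment would be used for teeth that are planned for extraction and additional teeth (10 total) in each participant". Oximeter readings cover the extraction teeth and up to 2 to 5 additional teeth. Histology is an exploratory outcome.
- Section 1.6, criterion 7, concerns the teeth that stay in the mouth: "Must have no history of spontaneous pain, and/or lingering pain to cold/hot in teeth that are not going to be extracted on that day".

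**The concern.** Sensitivity and specificity mean something only against a reference that is independent of the test being scored. Histology is such a reference, but only extracted teeth can have it. For the other teeth the plan names no reference. The one assessment it calls a gold standard in the clinic is cold and EPT, the tests whose accuracy 1.20 estimates. If that standard fills the gap, cold and EPT are partly graded against their own results.

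This bears on the main question. Section 1.22 sets out to compare the accuracy of traditional testing with that of the oximeter. In any tooth whose status comes from cold and EPT, each disagreement is scored as an oximeter error. The oximeter can then at best match the cold/EPT assessment and can never appear better, even where it is right.

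**Working it through.** The plan states no accuracy, prevalence or power figure, so there is nothing of its own to reproduce. Section 1.21 gives only 35 completers.

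**Step 1: share of tested teeth without histology.** Inputs: at least one extraction per participant (1.6, criterion 2) and up to 2 to 5 additional teeth (1.5, oximeter item). Assume every extracted tooth is collected and readable. Share = additional / (extracted + additional).
- One extraction: 2/3 = 67% to 5/6 = 83%. For 35 participants that is 70 of 105 teeth to 175 of 210.
- Two extractions: 2/4 = 50% to 5/7 = 71%.
- Section 1.5 gives 10 teeth in total for the conventional tests. On that count the share would be 9/10 = 90% with one extraction.

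**Step 2: illustration.** All inputs are assumed, none comes from the documents: true sensitivity 75%, specificity 90%; disease in 40% of extracted and 5% of additional teeth; *m* = 2 to 5 additional teeth per extracted tooth; cold/EPT treated as one test; extracted teeth labelled by histology.

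Per 100 extracted teeth: true positives 40 × 0.75 = 30, false negatives 10, false positives 60 × 0.10 = 6, true negatives 54.

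Per 100*m* additional teeth: test-positives = 5*m* × 0.75 + 95*m* × 0.10 = 3.75*m* + 9.5*m* = 13.25*m*; test-negatives = 86.75*m*.

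*Self-labelled.* All 13.25*m* positives count as true positives and all 86.75*m* negatives as true negatives.

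| | Apparent sensitivity | Apparent specificity |
|---|---|---|
| *m* = 2 | (30 + 26.5)/(40 + 26.5) = 85.0% | (54 + 173.5)/(60 + 173.5) = 97.4% |
| *m* = 5 | (30 + 66.25)/(40 + 66.25) = 90.6% | (54 + 433.75)/(60 + 433.75) = 98.8% |

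*Presumed healthy from symptoms.* Sensitivity stays at 75%, because no additional tooth enters the diseased group. All 13.25*m* positives become false positives, including the 3.75*m* that are truly diseased. Diseased teeth that the test misses count as true negatives. Specificity is (54 + 173.5)/(60 + 200) = 87.5% for *m* = 2 and (54 + 433.75)/(60 + 500) = 87.1% for *m* = 5, against a true 90%.

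**Step 3: other assignment rules.** A second model keeps cold and EPT as two tests of equal accuracy. Assumed: true sensitivity 0.80, specificity 0.90; disease in 50% of extracted and 5% or 20% of additional teeth; correlation between the tests, given true status, of 0 or 0.5; one extracted tooth and 2 or 5 additional teeth. Pooled results for one test:

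| Status of additional teeth taken from | Sensitivity (true 0.80) | Specificity (true 0.90) |
|---|---|---|
| the test itself | 0.87–0.94 | 0.98–0.99 |
| either test positive | 0.65–0.82 | 0.97–0.99 |
| both tests positive | 0.83–0.93 | 0.88–0.94 |
| presumed healthy | 0.80 | 0.77–0.87 |

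One cell as a check (either positive, 5% disease, correlation 0, 2 additional teeth). The test is positive in 0.05 × 0.80 + 0.95 × 0.10 = 0.135 of additional teeth. Either test is positive in 0.05 × 0.96 + 0.95 × 0.19 = 0.2285. Pooled sensitivity = (0.40 + 2 × 0.135)/(0.50 + 2 × 0.2285) = 0.670/0.957 = 0.70.

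Both measures are inflated with certainty only when a test is its own reference. With a composite, one measure is perfect in the additional teeth by construction, so at least one is inflated; the other may fall.

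**The case against.** The strongest reply is that 1.20 never says non-extracted teeth enter the accuracy calculation. Histology is the only source it names for true disease, and its disease group resembles the two worst histological classes (pulpitis and necrosis). The closing sentence might only be adding the clinical measurements other than heat, cold and EPT. This reading is possible. The way histology is introduced, as an addition and for extracted teeth only, makes it strained, but the text does not exclude it.

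A reader might infer more than the documents support:
- *That non-extracted teeth can only be labelled by cold and EPT.* Symptom history, the panoramic radiograph, percussion and palpation are also available for them. No section says that any of these assigns true status, but none rules it out.
- *That the plan inflates the accuracy of cold and EPT.* The direction depends on the rule, and an either-positive or presumed-healthy rule can lower one measure.
- *That a bias of known size against the oximeter is shown.* Section 1.20 lists no sensitivity or specificity for the oximeter. What follows is only that a cold/EPT reference leaves it no room to look better.
- *That unverified teeth are always the majority.* With two extractions and two additional teeth they are half.

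It is also fair that 1.5 presents the conventional diagnosis as a subjective measurement to be correlated, not as a reference. The gold-standard label comes from 1.22. That section does plan a comparison of clinical with histological status, but this does not define the reference used in 1.20.

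**Conclusion.** The concern holds as an undefined reference standard with a real risk of circularity, not as a proven circular design. Section 1.20 leaves open the source of true status and the teeth it covers, and 1.22 gives the label of gold standard to tests that 1.20 evaluates. Each rule examined here for the unverified teeth distorts at least one accuracy measure, so the choice cannot be left until the data are in. The distortion could be large: under the Step 2 assumptions, 10 to 16 percentage points of sensitivity and 7 to 9 of specificity if self-labelled, or about 3 points of specificity lost if presumed healthy. These sizes are illustrative. The unverified share rests only on the plan's tooth counts and an assumed one or two extractions per participant.

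**What to change.** In 1.20 and 1.22:
1. Define true status as the histological result, and state how the four histological classes map to the two groups. The transitional stage is currently unassigned.
2. Restrict every sensitivity, specificity and predictive-value table to extracted teeth with a histology result, using the same teeth for cold, EPT and oximeter.
3. Report non-extracted teeth separately, as agreement between oximeter and cold/EPT and as repeatability, and do not describe this as accuracy.
4. Stop calling Cold and EPT the gold standard.

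This changes wording and needs no new data. The cost is precision: about 35 verified teeth if each participant contributes one. At an assumed 40% disease that is 35 × 0.40 = 14 diseased teeth, and a sensitivity of 75% would have a 95% Wilson interval of roughly 49% to 90%. Predictive values would apply only to teeth selected for extraction, and the report should say so.

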1.21 Sample Size Considerations

35 completer in total

1.22 Final Analysis Plan

To compare accuracy of pulp vitality between traditional tooth vitality testing (Cold and EPT) to pulse oximeter reading to determine if the pulse oximeter is a reliable indicator of tooth vitality. We will analyze the relationships between these clinical readings using Pearson correlations and/or Chi Square tests. We will evaluate repeatability of the measurements within a tooth for the pulse oximeter using Bland-Altman plots, intraclass correlation coefficients (ICCs), and the percentage of repeat measurements within +/- 0.5 mm along with a 95% confidence interval for the percentage. Pulse oximeter reading will be compared against the gold standard (Cold and EPT) assessment using paired t-tests, 95% confidence intervals for the difference from the gold standard with a 95% confidence interval. The clinical pulpal status will be compared to the histological status for the difference using ANOVA and compared for the percentage of measurements with +/- gold standard visual assessment of the pulp status using McNemar's tests.

SOURCE DOCUMENTS AND ACCESS TO SOURCE DATA/DOCUMENTS

Study staff will maintain appropriate dental and research records for this study. Study staff will permit authorized representative and regulatory agencies to examine (and when required by applicable law, to copy) research records for the purposes of quality assurance reviews, audits and evaluation of the study safety, progress and data validity.

QUALITY CONTROL AND QUALITY ASSURANCE

Quality control will be continually monitored by periodic (semi-annual) reviews of the protocol and procedures used in the study. All questionnaire data is reviewed on the day of the participant visit for completeness. De-identified data is monitored after collection for various points of quality assurance.

ETHICS/PROTECTION OF HUMAN SUBJECTS:

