- *Laser Doppler Flowmeter (LDF):* Measurements obtained from LDF pulse oximeter gives a series of reading of blood velocity. LDF measurements would be used for teeth that are planned for extraction and also up to 2-5 additional teeth in each participant

STUDY DESIGN

Standard Care Procedures:

Participants may receive the following treatment procedures whether he/she join this study or not:

- Review of medical and dental history
- Oral examinations
- Dental Procedures (e.g., extractions) planned by his/her oral surgery provider

Study-Related Procedure

- The researcher will gather information initially by asking if any of the teeth are hurting or sensitive to hot/cold
- Participants will complete self-report questionaries' regarding their history of dental pain
- Existing panoramic radiograph will be reviewed by a member of research team prior to choosing which teeth (less than 10) will be to be tested.
- Blood pressure, and heart rate values would be recorded on this appointment from your medical record by a member of research team prior to the extraction.
- The researcher initially will palpate the gum around selected teeth and record any discomfort
- A plastic clip, pulse oximeter will be placed over the teeth, one at a time, to measure blood flow by measuring the presence of pulse in these teeth for approximately for 15-30 seconds.
- The clip will remain on the tooth for additional 2-3 minutes to continually measuring pulse while the following tests are taken place:
 - **Cold Testing**: This test is used to assess if the tooth is "dead" or "alive" by measuring sensation of cold from the tooth. A small cotton ball will be sprayed with cold spray (called Endo-Ice) and then placed on the surface of that tooth for approximately 15 seconds or till participant reports any sensation of cold. There would be 30 seconds wait time prior to the next step.
 - **Electrical Pulp Testing:** This test is used to assess if the tooth is "dead" or "alive" by measuring sensation of electrical pulses from the tooth. A small probe attached to an electrical pulp testing (EPT) device will be placed on the surface of that tooth for approximately 15 seconds or till participant reports any tingling sensation. There would be 30 seconds wait time prior to the next step.

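### Section 1.22 applies Pearson correlation and paired t-tests without saying how an absent pulse or absent response is coded, or which of Pearson and chi-square applies

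*Combined protocol and SAP*

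**What the plan says.** Section 1.5 (Study Outcome Measures) names the primary outcome as "Correlation Between Subjective and Objective Measurements of Pulpal Status". The subjective side is cold, EPT, percussion and palpation; the objective side is the pulse oximeter.

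The oximeter result is described in two ways. Section 1.5 treats it as numeric: "Measurements obtained from pulse oximeter gives a series of reading of oxygen saturation level, and pulse". The Study Design section treats it as present or absent: the clip is used "to measure blood flow by measuring the presence of pulse in these teeth".

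Cold and EPT each end at first sensation or at a time limit. The EPT probe is applied "for approximately 15 seconds or till participant reports any tingling sensation", and the cold test has the same 15-second limit.

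For the analysis, section 1.22 says "We will analyze the relationships between these clinical readings using Pearson correlations and/or Chi Square tests", without assigning either method to any variable. It then says "Pulse oximeter reading will be compared against the gold standard (Cold and EPT) assessment using paired t-tests". McNemar's test is named for clinical against histological status. Section 1.20 plans sensitivity, specificity and predictive values for heat, cold and electrical tests; the oximeter is not named. Form 2 has one reading field per test and no code for an absent result.

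**The concern.** The study asks whether a tooth is alive or dead. Section 1.1 explains that the oximeter depends on the pulsatile arterial signal, so a tooth without a detectable pulse may yield no saturation value. A tooth that feels nothing by the time limit has no response value, or at most a limit value. An absent reading can therefore be the most informative result a test gives.

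Pearson correlation and the paired t-test cannot use such a result until someone decides what number, if any, stands for it. The plan leaves that decision open, along with the choice between Pearson and chi-square. Both could be settled after the data are seen, and the primary result depends on them.

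**Working it through.** There is no planned figure to reproduce. The plan states no expected correlation, and section 1.21 gives 35 completers without inputs.

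**Step 1. What each planned method does with a tooth that has no reading**
- Pearson: needs a number from both tests; no rule is given.
- Paired t-test: the same. It also subtracts quantities in different units (saturation against a cold or EPT result), so the difference has no meaning under any coding.
- Chi-square: could keep the tooth as a category, but neither a no-pulse category nor an oximeter cut-off is defined.
- McNemar: could also keep it, but needs the same missing definition.

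**Step 2. How far the coding rule moves the result**

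All inputs here are assumptions; none is in the documents.
- The share p of non-vital teeth is 10%, 30% or 50%.
- Each test gives no reading in 90% of non-vital and 10% of vital teeth, independently given status.
- Vital readings are saturation 85 (SD 5) and EPT 35 (SD 12), with an EPT limit of 80, uncorrelated among vital teeth.
- Teeth are treated as independent.

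Let m = 0.9p + 0.1(1-p) be the share without a reading on one test, b = 0.81p + 0.01(1-p) the share without a reading on both, and c = b - m².

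- Left blank: the usable share is 0.81(1-p) + 0.01p. Only 1% of non-vital teeth remain, and r is the vital-tooth value, 0.
- Coded as saturation L and EPT 80: r = -(85-L)·45·c / √{[(85-L)²m(1-m) + 25(1-m)]·[45²m(1-m) + 144(1-m)]}.
- 2x2 table: phi = c / [m(1-m)].

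For p = 30%: m = 0.34, b = 0.25, c = 0.25 - 0.1156 = 0.1344, m(1-m) = 0.2244.
- Blank: the usable share is 0.57, so 35 teeth become about 20 pairs.
- L = 0: r = -(3825 × 0.1344)/√(1637.8 × 549.4) = -514.1/948.6 = -0.54.
- L = 70: r = -(675 × 0.1344)/√(67.0 × 549.4) = -90.7/191.8 = -0.47.
- phi = 0.1344/0.2244 = 0.60.

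| Non-vital share | Usable pairs of 35 if blank | r, blank | r, coded 0 and 80 | r, coded 70 and 80 | phi, all teeth |
|---|---|---|---|---|---|
| 10% | about 26 | 0.00 | -0.33 | -0.26 | 0.39 |
| 30% | about 20 | 0.00 | -0.54 | -0.47 | 0.60 |
| 50% | about 14 | 0.00 | -0.60 | -0.54 | 0.64 |

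Simulation (3,000 data sets per setting, 35 or 140 teeth) agrees with these values to about 0.01. With a vital-tooth correlation of -0.3, leaving readings blank gives about -0.30 at every share, and the 0-and-80 coding gives about -0.34 to -0.61.

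**Step 3. What if few teeth lack a signal?**

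Take 100 vital teeth with no association among them, plus k teeth with neither pulse nor response. Pearson on teeth with readings averages 0.00. Spearman with the k teeth tied at the worst rank is -B/(B + W), where B = 100·k·(100+k)/4 and W = 100(100² - 1)/12 = 83,325.

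- k = 20: B = 60,000, so -60,000/143,325 = -0.42.
- k = 2, 5, 10, 30: -0.06, -0.14, -0.25, -0.54.

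This is a best case: the two tests never disagree about absence, and no vital tooth loses its signal.

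**The case against.** The strongest reply is that the quoted sentence already offers chi-square, which keeps every tooth, and that McNemar's test is also planned. The Study Design section treats the presence of a pulse as the measurement and describes cold and EPT as tests of whether a tooth is alive, so absence is an intended result. Form 2 has an open reading field, and nothing prevents an examiner from writing 'none'. All of this stands, but it does not close the gap: the choice of method is open, and the category or cut-off needed to build the oximeter table is not defined.

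A reader might infer three stronger points that the documents do not support.
- That teeth without a reading are dropped. No section says so; omission follows only if the fields are left blank.
- That a tooth without a signal is a dead tooth. Placement can fail: the holder is a first design with a 5-8 mm interface layer. The disease group in section 1.20 also includes irreversible pulpitis.
- That the planned accuracy figures share the problem. Section 1.20 names them for the conventional tests, which can be scored positive or negative without a numeric value.

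It is also fair to say that the documents give no prevalence of non-vital teeth, no EPT scale, and no statement of what the device shows without a pulse. The size of the effect is therefore not known for this study.

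**Conclusion.** The concern holds as a missing rule. Section 1.22 applies methods that need two numbers to tests whose key result may be no number, and it leaves both the coding and the choice between Pearson and chi-square open. Under the stated assumptions the correlation on the same teeth runs from about 0 (left blank) to about -0.6 (limit values entered, half the teeth non-vital), and to about -0.3 at 10% non-vital. With only a handful of teeth lacking a signal, the effect is small. These figures rest on assumed tooth counts, error rates and reading scales; they show sensitivity to the rule and do not predict the trial's result. The unit mismatch in the paired t-test rests on no assumption.

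**What to change.** **Cheap improvement**, in section 1.22 and Form 2:

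1. Record an absent pulse and an absent response as explicit results on Form 2, with a mark for suspected placement failure. Keep these teeth in every denominator.
2. Make the 2x2 response-by-pulse table the main analysis of the primary outcome. Replace Pearson with a rank correlation that places absent readings at the worst rank. If a saturation cut-off is to define the oximeter result instead of presence of a pulse, state it in advance.
3. Replace the paired t-test of the oximeter reading against cold and EPT with McNemar's test on the binary results. McNemar compares only the rates of positive results, so read it beside the 2x2 table, which shows tooth-by-tooth agreement.
4. For extracted teeth, report counts without a signal by histology class, with a sensitivity analysis that excludes marked placement failures.

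The cost is analysis-plan wording and a small form edit; no procedure or participant is added. The downside is that technical failures in healthy teeth may lower the oximeter's apparent specificity by an unknown amount. The sensitivity analysis in item 4 would show this.

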 - **Percussion Testing:** This test is used to assess if the tooth is "dead" or "alive". The end of the mouth mirror is used to gently tap on the tooth surface and record any discomfort. There would be 30 seconds wait time prior to removal of the clip.
 - 0
- Once the tests above are completed, the plastic clip will be removed from your tooth. The pulse oximeter sensors will be removed from the plastic clip and replace with the LDF sensor. The plastic clip will be placed back over the teeth previously tested to measure the blood flow with the LDF. Blood flow will be measured by the presence of a pulse in each tooth for approximately for 15-30 seconds. Once the measurement is obtained, the plastic clip will be removed from the tooth.

- After obtaining participant's permission, researchers will obtain a de-identified copy of the participants dental radiographs
- After planned extraction is completed by the oral surgery provider, the tooth/teeth from the standard of care procedure will be provided to the researcher for further analysis to determine of the tooth is "alive or dead". This process will occur at the University of Michigan School of Dentistry Oral Surgery Clinics.
- Upon completion of extraction, the teeth will be placed in formalin-containing bottle. After formalin fixation, the teeth will be prepared for histological examination using 10% EDTA for demineralization. Following that, the teeth are trimmed, embedded in paraplast and cut longitudinally to obtain 6um thick section. The sections were stained with H&E and examined with a light microscope. The histological diagnosis are based on the classification used by Seltzer et al. as follow:
 - 1. Normal Pulp: Intact, uninflamed pulp
 - 2. Transitional Stage: Intact pulp with scattered inflammatory cells
 - 3. Pulpitis: inflammatory process affecting the coronal and radicular
 - 4. Pulp Necrosis: All pulp tissue is necrotic

STUDY ENROLLMENT AND WITHDRAWAL

1.6 **Subject Inclusion Criteria**

In order to be eligible to participate in this study, you must meet the following criteria:

- 1. Must be a patient of the University of Michigan School of Dentistry Oral Surgery Clinics
- 2. Must be scheduled for at least one tooth extraction at Oral Surgery Clinic
- 3. Must be 18 to 65 years old
- 4. Must be able to understand and willing to cooperate with all study procedures
- 5. Must be able to sign an IRB-approved written consent

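### Section 1.22 asks whether the pulse oximeter is a reliable indicator of vitality, but tests only for non-zero association and plans no accuracy estimate for the device

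*Combined protocol and SAP*

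**What the plan says.** Section 1.5 names the primary outcome: "Primary Outcomes Measures: Correlation Between Subjective and Objective Measurements of Pulpal Status". The objective measurement is the oximeter's oxygen saturation and pulse. The subjective ones are the cold test and EPT, with percussion and palpation.

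Aim 4 (sections 1.2 and 1.4) is "To evaluate the relationships between the Aims 1-3 to determine if pulpal blood flow is a reliable indicator of tooth vitality". Section 1.22 repeats the purpose for the device itself, "to determine if the pulse oximeter is a reliable indicator of tooth vitality", and follows it with "We will analyze the relationships between these clinical readings using Pearson correlations and/or Chi Square tests".

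The plan contains other analyses that bear on the point:

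- Section 1.20 plans sensitivity, specificity, PPV and NPV, but the tests it lists are heat, cold and electrical pulp testing. It adds a general comparison of clinical measurements on extracted teeth with histology.
- Section 1.22 has Bland-Altman plots, ICCs and a percentage within limits for repeat oximeter readings within a tooth.
- Section 1.22 has paired t-tests and confidence intervals for oximeter against Cold/EPT.
- Section 1.22 has ANOVA and McNemar tests for clinical pulpal status against histology.

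The sample size section reads, in full, "35 completer in total". No alpha, target precision or minimum acceptable performance is given.

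**The concern.** Reliability as an indicator is a question of how often the device is right: how many non-vital teeth it flags and how many vital teeth it clears. Pearson and chi-square tests address whether two readings are unrelated. With enough teeth, a weak relationship is significant.

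Section 1.20 itself presents sensitivity, specificity and predictive values as the way to characterise a test, yet leaves out the device under study. The trial could therefore end with accuracy figures for the established tests and only a measure of association for the oximeter. Aim 4 would be unanswered. Section 1.2 looks ahead to using the method to decide which teeth need treatment, so an overstated conclusion would matter.

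**Working it through.** **1. The plan's own figure.** The stated size is 35 completers. No alpha, power, effect size or precision target accompanies it, so it can be neither reproduced nor refuted.

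**2. Number of teeth.** The oximeter is planned as follows: "Pulse oximeter measurements would be used for teeth that are planned for extraction and also up to 2-5 additional teeth in each participant". Section 1.6 requires at least one scheduled extraction. One extraction tooth plus 2 to 5 others is 3 to 6 teeth per person, so 35 × 3 = 105 to 35 × 6 = 210 teeth. Form 2 as supplied has four tooth blocks, giving 35 × 4 = 140. The conventional tests cover "additional teeth (10 total) in each participant". One tooth per person gives 35.

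**3. Smallest significant correlation** (two-sided 5%, assumed): r = t / √(n − 2 + t²), with t the 97.5th percentile on n − 2 degrees of freedom.

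| Teeth | Smallest significant r | Shared variance r² |
|---|---|---|
| 35 | 0.33 | 11% |
| 105 | 0.19 | 3.7% |
| 140 | 0.17 | 2.8% |
| 210 | 0.14 | 1.8% |

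**4. Chi-square with a poor device.** Assumptions, none given in the documents: teeth independent; 25% do not respond to Cold/EPT; the oximeter shows no pulse in 50% of those (sensitivity 50%); specificity varied. Power of the uncorrected two-sided 5% chi-square, summed exactly over the possible 2×2 tables:

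| Specificity | 35 teeth | 105 | 140 | 210 |
|---|---|---|---|---|
| 80% | 42% | 83% | 92% | 98% |
| 70% | 20% | 47% | 57% | 74% |
| 60% | 9% | 15% | 18% | 25% |

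Hand check at 80% specificity and 105 teeth:

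- Share with no pulse: 0.25 × 0.50 + 0.75 × 0.20 = 0.275.
- phi = (0.50 − 0.20) × √[0.25 × 0.75 / (0.275 × 0.725)] = 0.291.
- √(105 × 0.291²) = 2.98, so power is about Φ(2.98 − 1.96) = 85%, close to the exact 83%.

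Agreement for this device: observed 0.25 × 0.50 + 0.75 × 0.80 = 0.725; by chance 0.25 × 0.275 + 0.75 × 0.725 = 0.6125; kappa = (0.725 − 0.6125) / (1 − 0.6125) = 0.29.

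**5. Clustering.** With four teeth per person the design effect is 1 + 3 × ICC. For ICC 0.1, 0.3 and 0.5 this is 1.3, 1.9 and 2.5, so 140 teeth count as about 108, 74 and 56. The 92% at 80% specificity then falls to about 84%, 69% and 58%.

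**6. Do the other analyses supply the missing estimate?**

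- Repeatability compares the oximeter with itself.
- A paired t-test asks whether a mean difference is zero. It does not count missed teeth.
- ANOVA compares mean levels across groups.
- McNemar asks whether the two kinds of disagreement are equally frequent. If 25% of teeth are non-vital, sensitivity is 50% and specificity is 83.3%, then missed teeth are 0.25 × 0.50 = 12.5% of all teeth and false alarms are 0.75 × 0.167 = 12.5%. McNemar's null is exactly true although half of the non-vital teeth are missed.

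**The case against.** The strongest reply is that the plan sets no decision rule. A reader might infer that p<0.05 will be taken as proof of reliability, but no section says so. The primary outcome is named as a correlation, and Pearson's r is a signed effect size, so a wrong-direction relationship would be visible. This stands. It narrows the point to what a significant result can support; it does not supply a criterion or an accuracy estimate.

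A second reply is that Pearson/chi-square is not the whole plan. Section 1.20 compares clinical measurements on extracted teeth with histology, and section 1.1 describes the blood-flow readings as clinical indicators, so the oximeter is arguably covered. That is fair as far as it goes. However, the accuracy measures are assigned by name to heat, cold and EPT, and the histology tests in 1.22 do not yield sensitivity or specificity.

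A reader might also infer that a device missing half of the non-vital teeth would usually be significant. The documents do not support that in general. It depends on tooth-level analysis and on specificity of about 80% or better, neither of which is stated. At 35 teeth, or at 70% specificity with 105 teeth, it is less than even.

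Finally, non-responding is not the same as non-vital. The protocol summary bases vitality on vascular supply rather than sensory fibres, so the figures above concern agreement with Cold/EPT only.

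**Conclusion.** The concern holds in this form. The analyses planned for the oximeter can show association with Cold/EPT and repeatability, but they do not estimate its accuracy. Significance would not justify calling it a reliable indicator. This follows from what the tests examine and does not depend on the scenarios.

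The size does depend on them. For sensitivity 50% and 25% non-responding teeth, significance ranges from 9% (35 teeth, specificity 60%) to 98% (210 teeth, specificity 80%), and is lower after adjustment for clustering. Alpha, specificity, the share of non-responding teeth, the ICC and the number of teeth analysed are all assumptions. The percentages should not be set against a nominal 5%, because these devices have a real association with Cold/EPT.

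The change should be made: it is cheap, and the data needed are already planned.

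**What to change.** In sections 1.20 and 1.22, with matching wording in 1.5:

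- Add the oximeter to the sensitivity, specificity, PPV and NPV analysis, with histology as reference for extracted teeth. State how the four histological classes map to the two groups in 1.20.
- For all tested teeth, report oximeter against Cold/EPT as agreement, not accuracy: kappa, the percentage of non-responding teeth with no pulse, and the percentage of responding teeth with a pulse.
- Give 95% intervals that allow for several teeth per participant, for example a bootstrap resampling participants.
- Fix the definition of a positive oximeter result before data lock. Keep saturation as a continuous reading as well, for example in an ROC curve.
- Base any reliability statement on these estimates and their lower confidence limits, against a minimum that the investigators set and justify in advance. Keep Pearson/chi-square as descriptive evidence of association.

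The cost is wording and some analysis time, with no new participants or measurements. The drawback is precision. Detecting 10 of 20 non-vital teeth gives an exact 95% interval of 27% to 73% for sensitivity before clustering. A favourable conclusion also becomes harder to reach. For example, suppose the Wilson lower limit for sensitivity must exceed 50%. With 25% non-responding and independent teeth, a device with 80% sensitivity passes in only 42% of trials at 35 teeth and 91% at 105. A device with 50% sensitivity passes in 2% to 3%. The minimum should be chosen with this in view. The number of teeth with histology is also not fixed, because sections 1.6 and 1.31 limit collection to extracted teeth that qualify.
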